## ***10.5. Required Concomitant Medications***

Protocol-required concomitant medications must be reported in the electronic case report form (eCRF) from the time of the pre-procedure visit through the 12 month follow-up. Information pertaining to the use of antiplatelet medications including dose changes, medication interruptions, and medication cessation, must be documented. Additional concomitant medications may be prescribed at the discretion of the investigator based on the standard clinical practice.

Antiplatelet medications such as P2Y12 inhibitor (Clopidogrel) and acetylsalicylic acid (ASA) are administered before the procedure, to minimize thrombotic complications and development of restenosis. Clopidogrel is recommended, unless it is not tolerated by the subject, then other antiplatelet medications or low-dose rivaroxaban (2.5mg twice per day) can be used.

For subjects who are intolerant to aspirin, alternative antiplatelet medications according to investigator's discretion, such as 300mg of clopidogrel.

### ***10.5.1. Prior to the index procedure***

- For subjects who have been taking dual antiplatelet therapy (DAPT) for  $\geq$  72 hours at the time of the index procedure, a loading dose is not required.
- For subjects who do not already take DAPT drugs for  $\geq$  24 hours at the time of index procedure should receive appropriate loading doses before the index procedure. Recommended loading doses are 300 mg of ASA and 300 mg of clopidogrel.

### ***10.5.2. In the Catheterization Laboratory***

- At the time of the procedure, subjects should receive an intra-arterial bolus of heparin (usually 3000-5000 IU), or alternate anticoagulants as substitutes for heparin if justified by individual subject conditions.

### ***10.5.3. Post-procedure***

- Subjects shall receive DAPT during a period of at least 6 months post the index procedure, if tolerated. The typical recommended DAPT regimen consists of ASA (minimum 75mg/d) and a P2Y12 inhibitor, e.g. clopidogrel (minimum 75mg/d).
- Alternate DAPT regimens may be followed if justified by individual subject conditions, e.g. if there is documented intolerance to any of these drugs, or the subjects already in a different antiplatelet therapy (with at least 2 approved drugs) due to comorbid conditions. The investigator shall be guided by the drug manufacturer's instructions, available scientific evidence and medical guidelines applicable to subjects with peripheral arterial disease.
- After 6 months of DAPT post procedure, all subjects are suggested to be treated with ASA (minimum 75 mg/d) indefinitely. For subjects who are intolerant to aspirin, alternative antiplatelet medications according to investigator's discretion, such as 300mg of clopidogrel.

**Note:** The risk of bleeding may be increased in the subjects who need anticoagulation in addition to DAPT. If needed, oral warfarin and low-dose rivaroxaban (2.5mg twice per day) can

be used, but no other new generation of oral anticoagulants, such as apixaban or dabigatran is allowed. subjects receiving anticoagulant therapy **should not** receive additional antiplatelet therapy if, in the opinion of the investigator, this could present an intolerable bleeding risk.

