Required Medication Therapy	
 
• If subjects have not already taken acetylsalicylic acid (ASA) (minimum 75 mg per day) and Clopidogrel (75 mg/day) or ticlopidine (200 mg/day) for at least 24 hours prior to the procedure, they will receive loading doses of 300 mg ASA and 300 mg Clopidogrel before the index procedure.
 
• At the time of the procedure, subjects receive an intra-arterial bolus of heparin (usually 3000-5000 IU).
 
• Subjects shall receive DAPT during a period of at least 6 months post the index procedure, if tolerated.
 
• After 6 months of DAPT post procedure, all subjects are suggested to be treated with ASA (minimum 75 mg/d) indefinitely. For subjects who are intolerant to aspirin, alternative antiplatelet medications according to investigator's discretion, such as 300mg of clopidogrel.
 
 
Note: The risk of bleeding may be increased in the subjects who need anticoagulation in addition to DAPT. If needed, oral warfarin and low-dose rivaroxaban (2.5mg twice per day) can be used, but no other new generation of oral anticoagulants, such as apixaban or dabigatran is allowed. subjects

Prospective, non-randomized, multicenter clinical study of the JETSTREAM™ Atherectomy System (Jetstream) in treatment of occlusive atherosclerotic lesions in the superficial femoral and/ or proximal popliteal arteries in Chinese patients (JETSTREAM CHINA)	
	
receiving anticoagulant therapy should not receive additional antiplatelet therapy if, in the opinion of the investigator, this could present an intolerable bleeding risk.

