	

6. Target lesion/vessel with in-stent restenosis

7. Subjects who have undergone prior surgery or endovascular intervention of SFA/PPA in the target limb to treat atherosclerotic disease within 3 months prior to the index procedure

8. Use of laser or any other debulking devices other than Jetstream System (such as CTO devices or cutting balloon) in the target limb during the index procedure

9. History of major amputation in the target limb

10. Documented life expectancy less than 12 months due to other medical co-morbid condition(s)

11. Known hypersensitivity or contraindication to contrast dye that, in the opinion of the investigator, cannot be adequately pre-medicated

12. Known history of coagulopathy or hypercoagulable bleeding disorder

13. Known hypersensitivity/allergy to the investigational devices or protocol related therapies (e.g., nitinol, stainless steel or other stent materials, and antiplatelet, anticoagulant, thrombolytic medications)

14. Platelet count < 80,000 mm^3 or > 600,000 mm^3 or history of bleeding diathesis

15. Undergoing hemodialysis or concomitant renal failure with a serum creatinine > 2.0 mg/dL (176.8umol/L)

16. History of myocardial infarction (MI), stroke/cerebrovascular accident (CVA) or gastrointestinal bleeding within 6 months prior to the enrollment

17. Unstable angina pectoris at the time of enrollment.

18. History of severe trauma, fracture, major surgery or biopsy of a parenchymal organ within past 14 days

19. Pregnant, breast feeding, or plan to become pregnant in the next 12 months

20. Current participation in another investigational drug or device clinical study that has not completed the primary endpoint at the time of enrollment or that clinically interferes with the current study endpoints (Note: studies requiring extended follow-up for products that were investigational, but have become commercially available since then are not considered investigational studies)

21. Septicemia at the time of enrollment

22. Presence of outflow lesions in the target limb requiring intervention during the index procedure

23. Presence of other hemodynamically significant lesions in the target limb requiring intervention within 30 days of enrollment

--	--

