Follow-up Schedule	Follow-up time points include: pre-discharge, 30 days, 6 and 12 months. All visits will be conducted in a clinic setting. Subjects who are enrolled but the Jetstream System is not used will be followed through the 30-day follow-up visit only.
Study Duration	The study will be considered complete after all subjects have completed the 12-month follow-up visit, are withdrawn from the trial (due to death or having been lost to follow-up) or their follow-up window (i.e., 30 days after a scheduled follow-up visit) has closed.
Required Medication Therapy	
 • If subjects have not already taken acetylsalicylic acid (ASA) (minimum 75 mg per day) and Clopidogrel (75 mg/day) or ticlopidine (200 mg/day) for at least 24 hours prior to the procedure, they will receive loading doses of 300 mg ASA and 300 mg Clopidogrel or 200 mg ticlopidine before the index procedure. • At the time of the procedure, subjects receive an intra-arterial bolus of heparin (usually 3000-5000 IU). • After the procedure, all subjects are recommended to be treated with ASA (minimum 75 mg per day) indefinitely, and with Clopidogrel (min 75 mg per day) or ticlopidine (200 mg) for 6 months. 
Note: a subject could be exempt of antiplatelet requirements if he/she requires Coumadin or other similar anti-coagulant due to known comorbidities and in the opinion of the investigator the combination of dual anti-platelet therapy (DAPT) and anticoagulation could pose an intolerable bleeding risk.

Key Inclusion Criteria	1. Subjects age 18 and older

**Prospective, non-randomized, multicenter clinical study of the JETSTREAM™
Atherectomy System (Jetstream) in treatment of occlusive atherosclerotic lesions in the
superficial femoral and/ or proximal popliteal arteries in Chinese patients
(JETSTREAM CHINA)**

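### The example alternative to long-term aspirin for aspirin-intolerant subjects is 300 mg of clopidogrel with no frequency; this matches the loading dose and is probably a dose error

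*Protocol*

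**What the plan says.** The last bullet of Protocol 10.5.3 covers the period after dual antiplatelet therapy (DAPT). It suggests aspirin at 75 mg per day or more, and the text then runs "indefinitely. For subjects who are intolerant to aspirin, alternative antiplatelet medications according to" the investigator's "discretion, such as 300mg of clopidogrel". The protocol synopsis (Required Medication Therapy) has the same sentence in the same position.

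The general text of section 10.5 repeats the phrase, but there it follows a paragraph about drugs given before the procedure.

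Other clopidogrel doses in the documents are:

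- Protocol 10.5.3, first bullet, typical DAPT regimen: "e.g. clopidogrel (minimum 75mg/d".
- Protocol synopsis, existing treatment that makes loading unnecessary: "Clopidogrel (75 mg/day) or ticlopidine (200 mg/day) for at least 24 hours prior to the procedure".
- Protocol 10.5.1: "Recommended loading doses are 300 mg of ASA and 300 mg of clopidogrel".
- SAP synopsis, post-procedure regimen: "with Clopidogrel (min 75 mg per day) or ticlopidine (200 mg) for 6 months". The SAP synopsis also gives 300 mg of clopidogrel as a loading dose. It does not contain the sentence on aspirin intolerance.

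**The concern.** The sentence stands in for an open-ended daily drug, so a reader expects a daily dose. It gives a single figure with no frequency, and that figure is the protocol's loading dose. Taken literally, it is either incomplete, because one 300 mg dose cannot replace continuing aspirin, or it invites 300 mg each day, which nothing else in the documents supports.

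What is at stake is the treatment of individual subjects. An investigator who looks to the protocol for a substitute finds only one worked example, and it is probably wrong. It sits in the operative treatment section and in the synopsis, under a title that calls the medication required.

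**Working it through.** No sample size, power or error rate is involved. The check is a comparison of texts plus one ratio.

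**Step 1. Clopidogrel doses side by side**

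| Place | Dose | Frequency given | Purpose |
|---|---|---|---|
| Protocol synopsis, before the procedure | 75 mg | per day | ongoing |
| Protocol synopsis, before the procedure | 300 mg | none | loading, so labelled |
| Protocol 10.5.1 | 300 mg | none | loading, so labelled |
| Protocol 10.5.3, first bullet | at least 75 mg | per day | ongoing, within DAPT |
| SAP synopsis, before the procedure | 75 mg | per day | ongoing |
| SAP synopsis, before the procedure | 300 mg | none | loading, so labelled |
| SAP synopsis, after the procedure | at least 75 mg | per day | ongoing |
| Protocol 10.5, general text | 300 mg | none | not stated; follows pre-procedure text |
| **Protocol synopsis and 10.5.3, after six months of DAPT** | **300 mg** | **none** | **alternative to continuing aspirin** |

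Every ongoing dose is 75 mg per day or a minimum of that. Every 300 mg dose with a stated purpose, apart from the last row, is a loading dose.

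**Step 2. Frequency within 10.5.3.** The other doses in that section all carry one: aspirin per day, clopidogrel per day, rivaroxaban 2.5 mg twice per day. Only the 300 mg figure has none. A loading dose needs no frequency, but a maintenance dose does.

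**Step 3. The repeat in 10.5.** Because it follows text on pre-procedure drugs, 300 mg may well mean a loading dose there. I do not count it as an error, although it should be labelled.

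**Step 4. Size, if the figure is read as daily.** The word daily is supplied by the reader and is not in the text.

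- Ratio to the protocol's minimum: 300 / 75 = 4.
- Difference: 300 − 75 = 225 mg per day.

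**Step 5. Timing against the endpoints.** The sentence applies after six months of DAPT, and follow-up ends at 12 months, so in-study exposure is roughly months 6 to 12. The stenosis endpoint is measured during the procedure, before any adjunctive therapy. The safety endpoint closes at day 30. Both are complete before the sentence applies.

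**Step 6. When the wording arrived.** The revision history places it in version AD, dated 21 October 2021. The first protocol release was in July 2017.

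**The case against.** The strongest reply is that nobody is told to give this dose. It is an example, it is left to the investigator, and the regimen it replaces is itself only suggested. The 75 mg figure is a minimum with no stated maximum, so 300 mg is not formally excluded. All of this stands, and it is why the point is a probable error in an example and not a mandated overdose.

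A second reply is that 10.5.3 already directs investigators to the manufacturer's instructions and to "available scientific evidence and medical guidelines applicable to subjects with peripheral arterial disease". That line belongs to the bullet on alternate DAPT regimens, which covers documented intolerance. A subject known to be intolerant would therefore probably have a guided regimen well before month 6. This lowers the risk. It does not clearly govern the later bullet, which sets its own example.

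A third reply is that few subjects are concerned. Exclusion criterion 13 removes those with known hypersensitivity or allergy to protocol therapies, including "antiplatelet, anticoagulant, thrombolytic medications". Other intolerance is not excluded, and the protocol would not need the sentence if it expected none.

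Stronger readings are tempting, but the documents do not support them:

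- **A fourfold overdose.** This needs a frequency that the text does not give.
- **A head count.** A reader might assume that 1% to 10% of about 80 subjects are intolerant and arrive at about 1 to 8. The documents give no such share. The sum also ignores criterion 13 and counts any subject who finished follow-up before version AD.
- **A bleeding risk that the protocol itself acknowledges.** Section 18.2 concerns prolonged dual therapy, and the note in 10.5.3 concerns anticoagulants added to it. Neither addresses the drug that replaces aspirin alone.
- **A wider flaw in treatment rules.** Section 7.5 allows balloon angioplasty after Jetstream, while 10.6.1 requires it. The second is probably the intent, performing it always satisfies both, and no effect on an endpoint or analysis set is shown.

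**Conclusion.** The concern holds as a probable dose error in the protocol synopsis and in 10.5.3. The documents' own usage supports this: 75 mg per day for every ongoing clopidogrel dose, and 300 mg otherwise labelled only as loading. That the figure was carried over from the loading text is an inference; the documents do not explain it.

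The number of subjects exposed cannot be derived. Neither primary endpoint, nor the sample size, power or significance level, is touched. The additional endpoints at 12 months overlap the period in time, but they are observational and no effect on them is shown. Section 10.5 requires antiplatelet use and dose changes to be recorded through 12 months, so any literal use of the example should be visible in the data.

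The text should be corrected for the safety of subjects. It does not threaten the trial's conclusions.

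**What to change.** In the protocol synopsis and in 10.5.3, replace the 300 mg example with a daily maintenance dose. The protocol's own figure is a minimum of 75 mg per day; the sponsor's medical team should confirm it. In the general text of 10.5, label 300 mg as a loading dose if that is what is meant.

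The cost is amendment wording, the ethics approval that section 13 requires for a change bearing on subject safety, and a notice to sites. No procedure, data item or analysis changes. Bringing 7.5 into line with 10.6.1 on balloon angioplasty could go into the same amendment as an optional clean-up.

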## 10.6. Enrollment & Index Procedure

Investigators will manage the cardiovascular risk factors and comorbidities for all subjects according to standard care. Investigators should ensure close monitoring of the amount of contrast for subjects with elevated serum creatinine levels and consider preventive measures (medication and hydration) to reduce the risk of contrast-induced nephropathy (CIN).

Diagnostic angiography of the lower extremities must be performed using standard techniques to confirm angiographic eligibility of the target lesion. Visual angiographic assessment may be used to determine if criteria are met.

Angiographic images must be sent to the Angiographic Core Laboratory for evaluation.

### 10.6.1. Treatment of target lesion

Procedural information must be reported (specific data fields are noted in the electronic database). Refer to the DFU for detailed instructions about preparation and treatment of Jetstream system.

The start of the index procedure is defined as the time of guide catheter insertion.

During the procedure, the following procedures and assessments must be completed:

- Perform angiography according to the Angiographic Core Laboratory procedure guidelines.
- Confirm angiographic eligibility criteria of the target lesion(s).
- Cross target lesion using guidewire, after target lesion is crossed by the guidewire within the true lumen, without a sub-intimal course based on visual assessment by operating physician, the subject will be considered eligible for enrollment.
- The use of body surface ultrasound will be strongly recommended for lesions such as CTO, when the guidewire is difficult to cross the lesion within the true lumen.
- Use of radiopaque rulers to document the exact distance of the lesion from a same anatomical landmark (such as the patella or the iliac or femoral bifurcation) at baseline and during follow-up visits is required.
- To evaluate the performance of Jetstream System exactly, pre-dilation of the target lesion prior to the treatment with Jetstream system is prohibited.
- Select an appropriately sized investigational Jetstream Catheter to adequately treat the target lesion and record the following information:
  - Baseline percent diameter stenosis (%DS) at the target lesion
  - Post atherectomy residual %DS at the target lesion
  - Information of Jetstream Catheter(s) used

- After the treatment with Jetstream System, PTA of the target lesions is required to be performed with optimally sized balloon(s) (nominal size of artery). Record the following information on PTA used:
  - Maximum balloon diameter (mm) inflated
  - Maximum pressure (atmospheres) inflated
  - Maximum length of time (seconds) inflated

### **Procedural recommendations:**

- Optimal target lesion/vessel treatment is recommended.
- Bailout stenting with a commercially-available stent or by-pass surgery may be performed at the discretion of operating physician, if the attempts with PTA have resulted any of the following:
  - Final residual stenosis at the target lesion being > 30% by visual assessment
  - Occurrence of Grade C or greater dissection (NHLBI)
  - Occurrence of clinically apparent perforation requiring treatments
  - Occurrence of any obstructive complication (e.g., recoil) demonstrating a marked decrease in the flow in the target vessel
- Angiographic complications, such as distal embolism or no reflow, should also be treated per standard practice. All angiographic complications during procedure should be documented by angiography and submitted to the Angiographic Core Laboratory for analysis.

### **Use of Jetstream System**

The DFU for the Jetstream System is provided in the Manual of Operations. Prior to use of the device, the treating physician must carefully read and be familiar with the entire DFU. The Jetstream system DFU must be followed for performing the device.

Anticoagulant therapy should be consistent with the hospital standard of practice during the procedure.

All clinical sites shall have access to an emergency unit to perform interventions as bypass surgery in case of failed PTA.

#### **10.6.2. Multiple Interventions during index procedure**

Please refer to **Section 7.3. Multiple Interventions Using Same Access Site during Index Procedure** for the treatment of contralateral iliac lesions and the non-target inflow lesions in the target limb.

#### **10.6.3. Post-procedure Angiogram**

Perform the post-procedure angiography according to the Angiographic Core Laboratory procedure guidelines. The final angiogram must be performed and recorded, including distal run-off. Angiographic images must be sent to the angiographic core laboratory for evaluation.

#### **10.6.4. End of the Index Procedure**

The end of the index procedure is defined as the time the guiding catheter was removed (post final angiography). The introducer(s) sheaths should be removed per standard local practice. The following procedures must be completed:

- Document procedural, target lesion, device information (Catheter/Console), PTA/stenting information on the appropriate eCRFs
- Record medications
- Record antithrombotic medications
- Complete AE assessment and collect source documents as described in Section 19.
- Finalize angiographic and related required documentation to submit to the Core Laboratories per instructions in the Manual of Operations

#### **10.7. Post-Procedure / Pre-Discharge**

The subject may be discharged from the hospital when clinically stable at the Investigator's discretion. The post-procedure/pre-discharge follow-up is an in-person visit and the following data will be collected prior to hospital discharge:

- Medication assessment
- AE assessment (any ongoing adverse events will be managed and treated by treating physicians per standard of care.)
- Duplex ultrasound (DUS) – optional (at the discretion of the investigator)

#### **10.8. 30-Day Follow-up (+/- 7 days)**

30-day follow-up is an in-person interview. The following data will be collected:

- ABI measurements
- Rutherford category assessment
- Medication assessment
- Adverse events (any ongoing adverse events will be managed and treated by treating physicians per standard of care.)

#### **10.9. 6-Month Follow-up (+/- 30 days)**

The 6-month follow-up is an in-person interview; and the following data will be collected:

- DUS of target lesion performed according to the DUS Core Laboratory procedure guidelines
- ABI measurements
- Rutherford category assessment
- Medication assessment
- Adverse events (any ongoing adverse events will be managed and treated by treating physicians

per standard of care.)

#### **10.10. 12-Month Follow-up (+/- 30 days)**

The 12-month follow-up is an in-person visit and the following data will be collected:

- DUS of target lesion performed according to the DUS Core Laboratory procedure guidelines
- ABI measurements
- Rutherford category assessment
- Medication assessment
- Adverse Events (any ongoing adverse events will be managed and treated by treating physicians per standard of care.)

**Note:** Use of rulers to document the exact distance of the lesion from a same anatomical landmark (such as the patella or the iliac or femoral bifurcation) at baseline and during follow-up visits is required.

